3.9 Summary of Background and Data on Linezolid

S. aureus bacteraemia remains a life-threatening condition with high morbidity and a mortality of up to 30% despite antibiotic therapy. Emerging evidence suggests that bacterial virulence factors significantly contribute to organ damage and poor patient outcomes. Linezolid, a well-established antibiotic with anti-virulence factor properties, offers a promising adjunctive treatment option. Preclinical studies demonstrate that linezolid effectively inhibits *S. aureus* virulence factor expression and improves survival in animal models. Clinical data support its safety and efficacy in various *S. aureus* infections, including pneumonia and bacteraemia.

Since its approval more than 20 years ago, the risk profile of linezolid has been well-documented. The approved treatment duration varies from 10-28 days depending on the cause and location of the infection. Notable adverse events of linezolid are myelosuppression, serotonin syndrome, kidney injury, *C. difficile*-associated diarrhoea, lactic acidosis, and neuropathy. Myelosuppression is typically associated with prolonged use (≥ 10 days) and is reversible upon linezolid discontinuation. Serotonin syndrome is very rare with monotherapy and remains uncommon even with concurrent serotonergic medications. Renal adverse effects including increased creatinine and rare cases of renal failure have been reported with linezolid use. Like many antibiotics, linezolid has been associated with *C. difficile*-associated diarrhoea, which can range from mild diarrhoea to fatal colitis. Lactic acidosis is rare but serious and is linked to extended treatment durations. Neuropathy has been described in patients with treatment durations exceeding the maximum recommendation of 28 days and is thus very unlikely to occur in this trial.

Since linezolid will be administered for only 5 days in the LIPS trial, a favourable safety profile is expected. In addition, hospitalization of study participants facilitates a close monitoring for any adverse events.

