³ Choose the result that represents the highest level recorded between day 6-14.

⁴ Linezolid trough concentration is only measured in a subset of participants in participating centres.

⁵ Adverse events of special interest until day 7 include: serotonin toxicity, myelosuppression, hyperlactataemia; until day 14: acute kidney injury; until day 90: C. difficile-associated diarrhoea.

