Acute kidney injury according to the modified Kidney Disease Improving Global Outcomes (KDIGO) stage 1 is defined as an increase in serum creatinine of $\geq 26.5 \mu\text{mol/L}$ from randomisation (baseline) to study day 5 or an increase in serum creatinine by 1.5 times or more the level of randomisation within 14 days of

randomisation. To collect this outcome, the serum creatinine at baseline (on randomisation day 1 or the calendar day prior to randomisation), day 5 (± 1 day), and only if participant remains hospitalised, at day 14 (± 3 days) will be documented in the eCRF. The values will be captured from available data in the hospital information system or from the participant's primary care physician, respectively.

- *C. difficile*-associated diarrhoea within 90 days.

The treating clinicians will assess for *C. difficile* infection based on the centre-specific diagnostic algorithm if clinical suspicion arises due to diarrhoea during antibiotic treatment. *C. difficile* infection will be evaluated on day 14, at discharge, and on day 90 by reviewing the participant's electronic health records. If a participant reports severe diarrhoea during a 90-day follow-up phone call, occurring after discharge and managed outside the centre, the responsible physician may be contacted to determine if a *C. difficile* infection was diagnosed.

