- Laboratory signs of myelosuppression until day 7: Participants will be monitored for signs of myelosuppression (thrombocytopenia, anaemia, leukopenia) as part of the clinical routine blood sampling. If blood count shows signs of myelosuppression, the local investigator will be involved to assess the potential causality between the IMP and the laboratory measurements. The local investigator will then decide if the participant needs to stop the intervention.
- Evidence of hyperlactatemia until day 7: In case of a clinical suspicion of hyperlactatemia, the local investigators must collect a blood sample to assess if the lactate level is above the upper norm according to specific laboratory-defined reference ranges. For increased lactate levels, the causality with the study treatment will be assessed. The local investigator will then decide if the participant needs to stop the intervention.
- Acute kidney injury: the kidney function is measured in the blood (creatinine) regularly as part of the clinical routine. To collect this outcome, the serum creatinine at baseline, on day 5 (± 1), and only if participant remains hospitalised, at day 14 (± 3 days) will be documented. The values will be captured from available data from the hospital information system.
- *C. difficile*-associated diarrhoea within 90 days: The treating clinicians will assess for *C. difficile* infection based on the centre-specific diagnostic algorithm if clinical suspicion arises due to diarrhoea during antibiotic treatment. *C. difficile* infection will be evaluated on day 14, at discharge, and on day 90 by reviewing the participant's electronic health records. If a participant reports severe diarrhoea during a 90-day follow-up phone call, occurring after discharge and managed outside the centre, the responsible physician may be contacted to determine if a *C. difficile* infection was diagnosed.

9.3.12 Assessment of serious adverse events and serious adverse reactions (from enrolment until discharge, and at day 90 ±7)

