All assessments of serious adverse events (SAE) and serious adverse reactions (SAR) during acute care hospitalisation will be part of the routine clinical work-up and monitoring of the participants. This generally includes a daily routine visit and evaluation of the participant by the treating physician. Further, the vital signs (blood pressure, pulse, body temperature, oxygenation) will be measured regularly by the nursing staff. Blood samples will regularly be taken to measure organ function (myelopoiesis, liver, kidney). For severely ill participants treated on the intensive-care unit, the clinical as well as laboratory evaluation is generally much more frequent. Any serious adverse event will be reported to the study-site principal investigator, who then assesses whether there is a reasonable causal relationship with the IMP. Assessment will take place from enrolment until acute care hospital discharge. Further, any post-discharge occurrence of an SAE/SAR will be assessed during the phone call at day 90 follow-up.

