9.3.14 Assessment of microbiological failure (day 28, discharge day, day 90 ±7)

“Early microbiological failure” and “microbiological failure” are defined as the identification of any new focus of *S. aureus* between 5 and 13 days, or 14 and 90 days after randomisation, respectively. This will be assessed by reviewing the participant’s microbiological results in the electronic health records. Any detection of *S. aureus* (by culture or by culture-independent methods such PCR) within the time frame will be further investigated in detail by reviewing the corresponding clinical health records. Thereby it can be determined – if necessary - whether the *S. aureus* originated from a sterile site. Any change of the initial antibiotic (and/or surgical) treatment plan will be analysed if it occurred due to proven detection of *S. aureus* at a sterile site. During the 90-day telephone call, it will be asked if any microbiological samples were taken outside of the corresponding centre. If this is the case, the responsible laboratory will be directly contacted to ask to provide the corresponding results. The principal investigator of each site will finally decide if a microbiological failure occurred. Furthermore, the independent outcome assessment board will review each documented microbiological failure on a case-by-case basis.

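### C. difficile-associated diarrhoea treated outside the centre after discharge has a narrower, optional route into the 90-day count than the same infection treated in the centre (minor)

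*Protocol*

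**What the plan says.** The synopsis, section 5.4 and section 9.2.4.1 all list C. difficile-associated diarrhoea as an adverse event of special interest over 90 days. A footnote to the schedule in 9.1 gives the window as "until day 90: C. difficile-associated diarrhoea". None of these places sets a severity threshold, and section 3.9 notes that the condition "can range from mild diarrhoea to fatal colitis". Mild and moderate cases therefore belong to the outcome.

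Sections 9.2.4.1 and 9.3.11 describe how cases are found, in the same terms:

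- Treating clinicians assess for "infection based on the centre-specific diagnostic algorithm if clinical suspicion arises due to diarrhoea during antibiotic treatment".
- The participant's electronic health record is reviewed on day 14, at discharge and on day 90. This step is prescribed and has no severity filter.
- For events after discharge and outside the centre, if the participant "reports severe diarrhoea during a 90-day follow-up phone call, occurring after discharge and managed outside the centre, the responsible physician may be contacted" to find out whether the infection was diagnosed.

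Section 9.3.14 handles a similar gap for microbiological failure differently. At the day-90 call "it will be asked if any microbiological samples were taken outside of the corresponding centre", and for each yes the protocol prescribes contact with the laboratory.

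**The concern.** The same confirmed infection can be counted or missed depending on where it was treated. In the centre, any grade is found by a prescribed record review. Elsewhere after discharge, the stated trigger is a report of severe diarrhoea, and even then contact with the physician is optional. A mild or moderate case diagnosed by a family doctor or in a rehabilitation clinic has no dedicated route into the outcome, although the outcome includes it.

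Time outside the centre is substantial by design. Section 8.7 expects antibiotic treatment of at least 2 to 6 weeks, and section 5.1 does not count rehabilitation or outpatient parenteral treatment as acute stay. Much of the 90-day window can therefore fall where the weaker rule applies. At stake is the completeness of one of five prespecified adverse events of special interest. Because it is reported descriptively, the count itself is the result.

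**Working it through.** **Two routes side by side (9.2.4.1, repeated in 9.3.11)**

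| | Seen in the centre's records | After discharge, outside the centre |
|---|---|---|
| Trigger | Record review on three occasions | Participant reports severe diarrhoea at the day-90 call |
| Severity filter | None | Severe |
| Verification | Prescribed | Optional |

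**What other parts of the protocol recover**

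- Serious outside cases: 9.3.12 states that "any post-discharge occurrence of an SAE/SAR will be assessed during the phone call at day 90 follow-up". Section 10.1 collects all SAEs throughout the study. Section 9.2.1 requires contact with the new hospital about potential SAEs after a transfer, and 10.1.3 requires follow-up of SAEs outside hospital that staff learn of. These cases are largely reached.
- Antibiotics after discharge: 9.2.2 adds a day-90 check for further prescriptions. It may reveal some C. difficile treatment but is not tied to this outcome.
- What remains is non-serious episodes managed wholly outside the centre, including severe but non-serious ones that are not reported or not checked.

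Every step in this gap loses cases and none adds any, so the bias is downward.

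**Size (illustration only)**

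The protocol gives no expected C. difficile rate, no share of cases after discharge and no capture probability. The only input from the documents is 303 participants per arm (11.2). The rest are assumptions.

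Let p be the true 90-day risk, f the share of cases arising after discharge and managed outside the centre, and c the share of those captured.

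Observed rate = p × [1 − f × (1 − c)], so the relative loss is f × (1 − c).

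*Narrower assumptions.* Between 30% and 60% of episodes arise after discharge and half of these are managed elsewhere, so f = 0.15 to 0.30. Of those, 50-70% are not severe and are lost, and all severe ones are captured.
- Low: 0.30 × 0.5 × 0.5 = 0.075, about 8%.
- High: 0.60 × 0.5 × 0.7 = 0.21, or 21%.
- With p = 3%: 303 × 0.03 = 9.1 events per arm, of which 0.7 to 1.9 are lost.
- With p = 1% to 5%: 3.0 to 15.2 events per arm, of which 0.2 (3.03 × 0.075) to 3.2 (15.15 × 0.21) are lost.

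*Wider assumptions.* f = 20-60%, c = 20-80%.
- Low: 0.2 × (1 − 0.8) = 0.04, or 4%.
- High: 0.6 × (1 − 0.2) = 0.48, or 48%.
- With p = 5%: 7.9 to 14.5 events are seen instead of 15.2.
- With p = 2%: 3.2 to 5.8 are seen instead of 6.1.

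**Between arms**

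With equal true risk and equal f, the apparent risk ratio is 1.00 whatever the value of c. A distortion needs f to differ by arm. If f were 50% with linezolid and 40% with placebo (assumed), the ratio (1 − 0.5(1 − c)) / (1 − 0.4(1 − c)) would be:
- c = 0.2: 0.60/0.68 = 0.88
- c = 0.5: 0.75/0.80 = 0.94
- c = 0.8: 0.90/0.92 = 0.98

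Nothing in the documents supports a 10-point difference in f. It only shows how the distortion would scale.

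**The case against.** The strongest defence is that the sentence in question adds a permission to a sound main rule. The record review has no severity limit and covers readmissions and outpatient visits at the centre. No sentence says that a non-severe outside diagnosis, once known, is to be left out. Serious cases are reached through SAE collection, and the antibiotic check may find others. Microbiological failure is an adjudicated part of the primary outcome, so stronger ascertainment there is proportionate in a pragmatic trial built on routine care and one call.

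Much of this stands. It limits the gap to non-serious outside episodes and lowers the importance of the point. It does not close the gap, because none of these routes reliably finds such an episode.

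Four stronger readings are tempting, and the protocol does not support them:

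- *Participants must volunteer the information.* The text is conditional on a report and specifies no question, but it does not rule one out.
- *Cases after the end of antibiotics are not counted.* The words "if clinical suspicion arises due to diarrhoea during antibiotic treatment" describe when clinicians test. The record review carries no such limit, and the outcome runs to day 90.
- *The rule favours linezolid.* The 20% shorter stay in 11.2 is a sample-size assumption about length of stay. It does not say where later diarrhoea is treated, and blinding otherwise makes the loss similar in both arms.
- *Post-discharge SAE/SAR capture has the same defect.* That is a separate matter. Reading 9.3.12 alone overlooks 9.2.1, 10.1 and 10.1.3.

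**Conclusion.** The point holds in limited form and is minor. The capture rule is narrower than the outcome it serves, so the 90-day rate of C. difficile-associated diarrhoea will tend to be understated in both arms. The direction follows from the text. The size does not: 8-21% and 4-48% of events rest entirely on assumed risks, shares and capture probabilities, and they show only that the loss could range from slight to material. A between-arm effect is speculative and probably small.

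Section 11.4.5 plans a descriptive analysis, so no formal comparison depends on this count. The sample size does not depend on it either. The primary outcome would be touched only if an episode were a serious adverse reaction or led to study drug discontinuation, and the non-serious, post-discharge episodes at issue here would hardly ever meet either condition.

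**What to change.** In 9.2.4.1 and 9.3.11, replace the last sentence on C. difficile with wording such as:

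> At the day-90 call, every participant or proxy will be asked whether they were tested or treated for C. difficile infection anywhere since discharge. For each yes, the responsible physician or laboratory will be contacted, and a confirmed infection of any severity will be counted.

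This follows the method of 9.3.14. It affects data capture only and leaves clinical testing and treatment as they are. The words about diarrhoea during antibiotic treatment can stay, and 9.3.12 needs no change for this point.

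The cost is a protocol wording change, one question in a call that already takes place, and a few extra contacts. Calls become slightly longer and the reported rate somewhat higher. The change is best made early, because cases missed in completed calls are hard to recover.

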9.2.4.2 Laboratory parameters

Blood sampling will be done according to clinical routine. Laboratory-specific adverse events will be measured as part of the clinical routine as outlined above. No additional tissue sampling or body fluids are necessary.

9.2.4.3 Vital signs

Vital signs are measured according to clinical routine. No additional study-specific vital sign measurements are necessary.

9.2.5 Assessments in participants who prematurely stop the study

Participants who withdraw from the study will receive further measurements as part of clinical routine. This includes all relevant assessments of adverse events.

9.3 Procedures at each visit

All visits except the 90-day follow-up will take place during the index hospitalisation and will be integrated or part of the clinical routine management of the participants.

9.3.1 Screening and identification of patients (Up to 72 hours before randomisation)

In patients suspected of having a bloodstream infection, blood is routinely drawn into blood culture bottles. These bottles are sent to the respective centre-specific laboratory for diagnostic microbiology to be incubated at approximately 37°C. When growth is detected in the bottles, pathogen identification diagnostics are initiated according to the laboratory-specific work instructions. If it is a case of *S. aureus* bacteraemia, blood culture bottles typically become positive (detection of bacterial growth in the bottle) after about 9 hours to 1 day of incubation.

Eligible patients will be identified by having positive blood cultures with *S. aureus*. Therefore, screening for eligible patients will primarily be done through regular review of the results of blood culture results sent to the diagnostic microbiology laboratory of each centre. Each centre will implement centre-specific procedures to ensure prompt notification of a positive blood culture result with *S. aureus*. This can occur through an electronic alert system or through other communication channels, depending on what is available and practical. Infectious diseases specialists of each centre are routinely involved in all patients with *S. aureus* bacteraemia. The goal is to identify potential participants as quickly as possible. Any microbiological identification method to identify *S. aureus* used in routine practice can be applied to positive blood cultures: PCR (polymerase chain reaction) results as well as other methods (e.g., MALDI-TOF: Matrix-Assisted Laser Desorption/Ionization-Time of Flight) are acceptable. PCR results (usually part of commercially available multiplex panel PCR) are typically available about 3 hours after detecting growth in the blood cultures; without PCR, pathogen identification is usually available within 24 hours.

9.3.2 Enrolment of participants (0-72 hours before randomisation)

Once a patient with *S. aureus* bacteraemia has been identified, the responsible centre-specific study team will assess whether the patient meets the inclusion criteria for the study. If this is the case, the site investigator or a delegated and study-specific trained person will approach the hospitalized patient. The patient will be informed

about the study and asked if they wish to participate. The patient should be given time to discuss any questions or uncertainties they may have. The patient will receive the informed consent form along with written explanations about the purpose and procedures of the study. Once the patient agrees to participate in the study, they will have to provide written consent by signing the appropriate form.

If a patient is unable to give an informed consent due to medical reasons (e.g., lack of consciousness due to severity of illness), a family member or a study-independent, treating physician should decide on the inclusion in the study on behalf of the patient. If the patient can be included, the patient representative should sign the corresponding informed consent form. When such a participant regains the ability to make decisions, the study inclusion will be reviewed with them by the study team, and a new informed consent will be signed. The participant may choose to withdraw from the study at any point.

The study team informs the care team (doctors, nursing staff) about the participant's participation in the study. Each centre will establish its own process how to distribute this information.

9.3.3 Randomisation (day 1)

Once a participant is enrolled via informed consent, the participant will be randomly assigned to a study arm through electronic randomisation within the REDCap® database. This will be initiated and coordinated by the local investigator (or designated personnel). All involved persons (participant, treating team, study team) will remain blinded to the allocation throughout the entire study duration – except in the case of emergency unblinding (see chapter 6.4 *Unblinding Procedures (Code break)*)

9.3.4 Assessment of baseline characteristics (day 1)

Most study-specific baseline characteristics are assessed as part of the clinical routine and can be extracted from the patient charts of each centre. The baseline characteristics include date of hospital admission, index blood culture, linezolid susceptibility, ethnicity, vital signs, polymicrobial bacteraemia (defined as more than one organism [at species level] in the index blood cultures, excluding those organisms judged to be contaminants by the treating clinicians), comorbidities, standard antibiotic treatment, markers of severity (mechanical ventilation, cardiac arrest, use of vasopressors, ICU), labour force status, injection drug use, and mental health diagnosis. The data closest to the time before start of the study treatment should be used. The study team of each site will check at the time of randomisation if all relevant information is available from the clinical routine assessment and – if necessary – will add the missing information by contacting the treating team or the participant directly. Together with the participant, the local investigator (or a delegated physician) will assess the level of function 4 weeks before randomisation. In case the participant is not able to provide this information, this data will be assessed at day 90 (asking about their level of function 4 weeks before their *S. aureus* bacteraemia).

9.3.5 Treatment (day 1 – day 5)

Each centre will implement the trial-specific procedures in accordance with local circumstances to ensure the administration and documentation of the study medication. The study medication should be prescribed and handled by the medical team in the same way as other oral medication during hospitalisation. The study team will hand over the study medication to the responsible medical treatment team on the respective ward. The study medication will be clearly labelled and stored in a designated location according to the centre's guidelines and prespecified workflow for the study. The study medication should be administered alongside the participant's other medications during hospitalization, generally by the nursing staff. The study medication should be administered as soon as possible once a participant has been enrolled and randomised. Thus, the first dose may also be given at night or at any time during the day. The study medication will be given twice daily for five days (in total 10 administrations) with approx. 12 hours interval between each administration. If maintaining a fixed 12-hour interval is challenging due to the start time (i.e., if subsequent doses would need to be administered in the middle of the night), the treating physician may adjust the interval according to standard practice. However, the interval should not be shortened or extended by more than 6 hours. It must be ensured that the start and stop of the treatment, the timing of each individual administration, and any missed doses are documented and can be traced for each participant. If a dose was not administered, the reason for this should be documented.

Most study-specific baseline characteristics are assessed as part of the clinical routine and can be extracted from the patient charts of each centre. The baseline characteristics include date of hospital admission, index blood culture, ethnicity, vital signs, comorbidities, standard antibiotic treatment, markers of severity (mechanical ventilation, cardiac arrest, use of vasopressors, ICU), injection drug use, and mental health diagnosis. The data

closest to the time before start of the study treatment should be used. The study team of each site will check at the time of treatment start if all relevant information is available from the clinical routine assessment and – if necessary – will add the missing information by contacting the treating team or the participant directly.

